**NCT Number**

**NCT06124131**

**Protocol Date:**

**3/11/2024**

## **Study Title: Building Engagement using Financial Incentives Trial – Colorectal cancer screening (BENEFIT-C)**

### **1. Study aim, background, and design**

Meta-analytic evidence suggests that **patient navigation** (which involves connecting patients with trained non-provider professionals who can guide them through the complexities of the healthcare system and provide tailored resources for overcoming barriers to accessing care) and **mailed stool-based screening kits** can improve the timely utilization of colorectal cancer screening, especially for populations experiencing health disparities. *Despite the strong evidence in support of these strategies for increasing patient engagement with preventive healthcare, low intrinsic motivation* among patients in real-world primary care settings may undermine the effectiveness of these evidence-based interventions. In light of low intrinsic motivation, extrinsic motivation in the form of **financial incentives** has been proposed to increase patient engagement with health behaviors. LA-CEAL will test the value of financial incentive-based interventions to increase engagement with preventive healthcare via the following objective:

**OBJECTIVE:** To determine if proven incentive-based interventions targeting SDOH as barriers to uptake of preventive healthcare and chronic disease management increase flu and COVID-19 booster vaccination, colorectal cancer screening (CRS), and hypertension-related health behaviors (self-monitoring of medication adherence, blood pressure, and sleep) in underrepresented minorities and rural communities.

Using a 2-arm randomized controlled trial design, we will test the effectiveness of patient financial incentives for enhancing routine outreach for preventive health services, namely colorectal cancer screening, flu vaccines, and COVID-19 vaccines. FQHC patients who are aged 45-75 years old and due for a colorectal cancer screening (up to n=100) will be identified through the electronic health records of our FQHC partners. Participants who meet eligibility criteria and enroll in the study will be randomized to one of two arms: the control arm will receive outreach by FQHC staff to encourage completion of a stool-based colorectal cancer screening provided by the FQHC as well as flu and COVID-19 vaccination. They will receive \$50 financial incentives/service for completion of flu and COVID-19 vaccines. The intervention arm will receive the same patient outreach and flu/COVID-19 incentives and will also be offered \$50 financial incentives for completion of colorectal cancer screening.

### **2. Subject Population**

Using the following criteria, we will enroll up to 100 patients at partner FQHCs:

Inclusion criteria: Age 45 to 75; receive care at a participating FQHC; due for a colorectal cancer screening; ability to understand and speak English

Exclusion criteria: currently participating in another clinical trial or research study on colorectal cancer screening; unable or unwilling to give informed consent

### **3. Procedure**

After obtaining verbal consent, FQHC outreach staff will verify eligibility and consent participants. The FQHC staff will then read either the intervention or control script depending on the random group assignment of each participant. The script for the control group will follow standard clinical practice for scheduling colorectal cancer screening (a stool-based test), flu and COVID-19 vaccination. The script will offer financial incentives (\$50 per service) for completing flu and COVID shots. The script for the intervention group will be adapted from the control script to include the offer of financial incentives (and additional \$50) for completion of colorectal cancer screening. Study staff will verify completion of each preventive service via weekly limited EHR data downloads for participating patients. After a 2-month follow-up period, a final EHR download will be obtained. The primary outcome is the difference in proportion of participants completing colorectal cancer screening between the two groups. All electronic data will be stored on secure cloud-based servers and accessed on HIPAA-compliant, encrypted, password-protected computers that are only accessible to the FQHC and study staff.

#### **4. Risks**

The risk of physical, psychological, social, or legal harm associated with participation in all components of this study is minimal:

- Participants may find it inconvenient to take time to participate in the study. All study activities will be arranged at a time that is convenient for participants. The option to complete study activities via telephone or Zoom will also ease the burden of participation for participants.
- There is a small risk of unauthorized disclosure of participants' responses, which will be prevented by following a strict protocol for data handling and rigorous training of study staff:
  - No identifying data (e.g., name, address) will be recorded on study forms. Identifying data used for participant recruitment will be kept separate from study data and no linkage will exist.
  - All electronic study records will be stored with password-protection. All paper study records will be locked in a secure study office. Data will be accessible only by study staff with approval from the PI.
  - The data will be retained without identifiers in a secure location for possible use in a future project, which will be consistent with the original research purpose.
  - Data may be shared with the NIH or other researchers upon request. Any data shared with the NIH or other researchers will not contain identifying information.

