#### **6. Remuneration**

While participants will not receive remuneration for participating in the study (as participation does not entail any activities beyond normal clinical practice), they will receive \$50 gift cards for completing each of the following services: flu shot, COVID-19 shot. In addition, those who are randomly assigned to the intervention group will receive a \$50 gift card for completing colorectal cancer screening within two months of the call. These financial incentives comprise the intervention being tested in this study.

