#### **8. Consent process and documentation**

FQHC partners will query their EHR systems and provide a list of eligible patients and their contact information to their outreach staff, who will call patients, verify eligibility, and read a consent script over the phone. All participants will provide verbal consent over the phone. We are requesting a waiver of documentation of consent and a waiver of HIPAA authorization due to practical concerns of obtaining written consent over the phone and the minimal-risk nature of the study.

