**NCT Number**

**NCT06124131**

**Statistical Analysis Plan Date:**

**3/11/2024**

**BENEFIT-C Statistical Analysis Plan.** Analyses for the primary outcome will test the between-group difference in the proportion of participants who completed a colorectal cancer screening at 2-month follow-up. Secondary outcomes will test between-group differences in the proportion of participants completing a flu shot, COVID-19 shot, any of the three services, and all three services at 2-month follow-up. Analyses will use a chi-squared test of independence or a Fisher's exact test, as appropriate based on achieved cell sizes. We will also test for statistically significant between-group differences in baseline characteristics, and if necessary, adjust for them in a follow-up sensitivity analysis using multivariable logistic regression.

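### Does the promise of no link between recruitment identifiers and study data prevent the primary outcome from being assigned to arm?

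*Protocol*

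**What the plan says.** The confidentiality text is in Protocol section 4, in a list of measures against unauthorized disclosure of what participants provide: "Identifying data used for participant recruitment will be kept separate from study data and no linkage will exist". The sentence sets no time limit and names no key or key-holder. A later item in the same list says that data will be kept without identifiers for possible future use, and another says that shared data will carry none.

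The operational text is elsewhere:

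- **Recruitment (section 8).** The health centers query their EHR systems and "provide a list of eligible patients and their contact information to their outreach staff".
- **Allocation (section 3).** "The FQHC staff will then read either the intervention or control script depending on the random group assignment of each participant".
- **Outcome (section 3).** "Study staff will verify completion of each preventive service via weekly limited EHR data downloads for participating patients". Then: "After a 2-month follow-up period, a final EHR download will be obtained".
- **Incentive (section 6).** Every participant can earn a card for each of the two vaccines. The intervention arm can also earn one for "colorectal cancer screening within two months of the call".
- **Analysis.** Section 3 defines the endpoint: "The primary outcome is the difference in proportion of participants completing colorectal cancer screening between the two groups". The SAP repeats it with the time point: "Analyses for the primary outcome will test the between-group difference in the proportion of participants who completed a colorectal cancer screening at 2-month follow-up".

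**The concern.** The primary endpoint of this trial exists only as a join. Arm is created when an identified patient is telephoned, and completion is read later from that patient's EHR record. If nothing connects the two, the two-by-two table that the SAP proposes to test cannot be filled in.

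A reader who takes section 4 at face value could therefore conclude that:

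- no verified outcome can be attributed to an arm;
- successive weekly extracts cannot be matched to one another;
- the two-month window cannot be counted from each person's own call;
- gift cards cannot be issued to the right people.

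A further worry is that the team would work around the ban informally. For example, the staff who read the scripts, and so know the arm, might count completions themselves. That could introduce errors or put outcome classification in unblinded hands. If so, the treatment difference might be diluted or distorted.

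**Working it through.** The plan gives no figure to reproduce here. The check is to set the operational steps beside the privacy sentence and ask what each step needs.

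1. **Calling and allocating (sections 8 and 3).** The caller has a name and telephone number, and must know which script applies. Arm is attached to an identified person from the start.
2. **Weekly and final downloads (section 3).** The downloads are restricted to enrolled patients. That requires an enrollment list matched to EHR records until the final download.
3. **Gift cards (section 6).** The vaccine cards need completion status traced to a reachable person. The screening card also needs arm and call date.
4. **Primary analysis (SAP).** Arm and completion are needed for each participant. The secondary outcomes of any service and all three services need the three results joined within a person. The adjusted logistic regression needs baseline characteristics joined as well.

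Each step needs at least a coded link while follow-up lasts. An unlimited statement that there is none cannot be literally true for that period.

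The next question is which text would govern conduct. Section 3 is specific: it names who verifies, from what source, how often and for whom. That work cannot start without knowing which EHR records belong to participants. Section 4 is a general assurance whose subject is the identifying data used for recruitment, which section 8 describes as a contact list held by outreach staff. A team that carries out section 3 will hold a study number or equivalent, and the data set that reaches the analyst will contain arm and outcome for each participant.

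**The dilution argument.** Suppose a fraction m of records in each of two equal arms is placed at random in the other arm. Let p1 and p0 be the true completion proportions. The observed difference is then

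[(1 − m)p1 + m·p0] − [(1 − m)p0 + m·p1] = (1 − 2m)(p1 − p0).

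| Assumed m | Factor 1 − 2m | Assumed true difference of 20 points becomes |
|---|---|---|
| 0 | 1.00 | 20 points |
| 0.05 | 0.90 | 18 points |
| 0.10 | 0.80 | 16 points |

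The algebra is right. However, m, the equal allocation and the 20-point difference are all assumptions, and the documents give none of them. The documents also describe no process that would make m greater than zero. The workaround in which script readers count completions is not in the plan, and it conflicts with section 3, which gives verification to study staff. With the data flow as written, this inconsistency supplies no reason to move from the first row of the table.

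**The case for a change.** The strongest case for acting is that the sentence is false as written, and that it does some work. Section 4 offers it as a safeguard against disclosure, and section 8 cites minimal risk when asking to waive consent documentation and HIPAA authorization. A safeguard that cannot be followed is a weak support for that request.

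The milder readings do not fully rescue it. If the sentence was meant only for the retained data set, it does not say so, and a separate item already covers retention. If the health center holds the only key, that is still a link, and it is not described. The access statements do not settle the matter either: section 3 allows access by health center and study staff, while section 4 limits it to study staff approved by the principal investigator.

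Most of this stands as a comment on the privacy wording. It is a matter for whoever maintains the confidentiality text and the ethics submission. The consent pages were removed from the copy reviewed, so a coded key may be described there; this cannot be known.

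What does not stand is the step from awkward wording to a threat to the trial's result. That step requires the privacy sentence to override the Procedure section, and the team then to improvise something that the plan does not contain. Having completion classified by someone unaware of arm is a separate preference about outcome assessment, and a contradiction about linkage gives it no support.

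**Conclusion.** The inconsistency is genuine but minor, and it calls for no change to the plan. The unqualified denial of any link cannot literally hold during follow-up. The operational sections nevertheless presuppose a coded link for every participant, and any competent team would keep one. Rewording section 4 would leave the primary comparison, the choice between chi-squared and Fisher's exact test, the enrollment ceiling of 100 and the interpretation exactly as they are.

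The expected effect on the primary estimate is zero. This rests on one assumption: that study staff verify outcomes from the EHR downloads as section 3 describes. The 10% to 20% dilution applies only under an assumed misassignment rate of 5% to 10%, for which the documents offer no basis, so it should not be cited as the size of this problem.

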#### **5. Benefits**

If the BENEFIT-C financial incentives are found to be effective at increasing engagement with preventive health services, individuals randomized to the intervention could benefit from those services. In addition, the knowledge gained from the study may benefit society in general by providing evidence for a strategy to increase patient engagement with preventive healthcare, with ensuing benefits for reducing morbidity and mortality.

#### **6. Remuneration**

While participants will not receive remuneration for participating in the study (as participation does not entail any activities beyond normal clinical practice), they will receive \$50 gift cards for completing each of the following services: flu shot, COVID-19 shot. In addition, those who are randomly assigned to the intervention group will receive a \$50 gift card for completing colorectal cancer screening within two months of the call. These financial incentives comprise the intervention being tested in this study.

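### Does the protocol's account of the tested intervention misstate what is randomised, given that both arms are paid for flu and COVID-19 vaccination?

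*Protocol*

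**What the plan says.** Section 1 of the protocol describes a two-arm randomised trial that will "test the effectiveness of patient financial incentives for enhancing routine outreach for preventive health services, namely colorectal cancer screening, flu vaccines, and COVID-19 vaccines". It then defines the arms. Control patients get outreach plus $50 for each of the two vaccines. For the other arm it says: "The intervention arm will receive the same patient outreach and flu/COVID-19 incentives", with $50 for screening on top.

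Section 3 (Procedure) matches this: "The script for the intervention group will be adapted from the control script to include the offer of financial incentives", the addition being $50 for screening. It names one primary outcome, the difference between arms in the proportion screened.

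Section 6 (Remuneration) says that all participants receive $50 "gift cards for completing each of the following services: flu shot, COVID-19 shot", and that "those who are randomly assigned to the intervention group will receive a" further $50 card for screening within two months. It closes with "These financial incentives comprise the intervention being tested in this study".

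The SAP tests screening as the primary outcome. Its secondary outcomes are flu vaccination, COVID-19 vaccination, any of the three services and all three, each compared between groups at two months by a chi-squared or Fisher's exact test. It does not say how the secondary comparisons should be interpreted.

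**The concern.** The closing sentence of section 6 is in the plural and follows a list of three cards, so a reader may take all three to be under test. The opening of the design paragraph in section 1 can be read the same way. The only labelled objective does not settle the matter: it asks whether incentives "increase flu and COVID-19 booster vaccination, colorectal cancer screening (CRS), and hypertension-related health behaviors", which names vaccination as a target.

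No arm goes without the vaccine incentives, so no comparison between arms can estimate their effect at any sample size. Four of the SAP's five comparisons nevertheless involve the vaccines. Two misreadings would be at stake. A null flu or COVID-19 result could be reported as evidence that incentives do not raise vaccination. A positive composite could be reported as a general gain in preventive care when it came from screening alone.

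**Working it through.** The plan states no figure to reproduce for this point. The check has three parts.

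**1. The randomised contrast.** The inputs are the arm definitions in sections 1, 3 and 6, which agree.

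| Service | Intervention | Control | Difference |
|---|---|---|---|
| Flu shot | $50 | $50 | $0 |
| COVID-19 shot | $50 | $50 | $0 |
| Screening | $50 | $0 | $50 |
| Maximum total | $150 | $100 | $50 |

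The whole contrast is the screening offer. A flu or COVID-19 difference, if real, is an effect of that offer on vaccination.

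**2. How far the composites can move through screening alone.** The documents give no uptake rates, so every rate here is assumed. Let d be the effect on screening, with no effect on either vaccine and screening independent of vaccination. Then:

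- difference in any service = d × P(neither vaccine)
- difference in all three = d × P(both vaccines)

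With d = 20 points:

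| Uptake of each vaccine | Relation between vaccines | P(neither) | P(both) | Any service | All three |
|---|---|---|---|---|---|
| 20% | independent | 0.64 | 0.04 | 12.8 | 0.8 |
| 20% | fully overlapping | 0.80 | 0.20 | 16.0 | 4.0 |
| 60% | independent | 0.16 | 0.36 | 3.2 | 7.2 |
| 60% | fully overlapping | 0.40 | 0.60 | 8.0 | 12.0 |

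The last two columns are in percentage points. In a worked case, screening goes from 20% to 40%, flu uptake is 50% and COVID-19 uptake 30%, all independent. P(neither) = 0.5 × 0.7 = 0.35, so any service goes from 1 − 0.8 × 0.35 = 72.0% to 1 − 0.6 × 0.35 = 79.0%. P(both) = 0.5 × 0.3 = 0.15, so all three goes from 0.2 × 0.15 = 3.0% to 0.4 × 0.15 = 6.0%.

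These ranges are not bounds. If the two vaccines overlap as little as possible, the any-service difference is 0 at 60% uptake each, because everyone has at least one vaccine. The all-three difference is 0 at 20% uptake each, because no one has both.

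**3. Whether the text misstates the contrast.**

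- *The plural.* Sections 1 and 3 both use the plural for the single $50 screening payment. The plural in section 6 therefore does not show that three cards are meant, and the sentence just before it concerns the card reserved for the randomised intervention group.
- *The paragraph's purpose.* Section 6 opens by saying that taking part is not paid. Its last line can be read as separating incentives from remuneration.
- *The design paragraph.* The list of services in section 1 may simply describe what the outreach covers.
- *The objective.* It belongs to the wider programme and includes hypertension behaviours that this trial does not study.
- *The other anchors.* The title names colorectal cancer screening, eligibility turns on being "due for a colorectal cancer screening; ability to understand and speak English" without mention of vaccination status, and the only primary outcome is screening.

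**The case for a change.** The strongest argument for a change is that a plan should fix interpretation before results are known. That a careful reader can infer the contrast is not the same as stating it. The one sentence that names the tested intervention is ambiguous, no labelled trial-level objective corrects it, and the SAP leaves the meaning of four of its five comparisons unstated. A sentence in each of a few sections would close the gap, and the only loss would be a claim that the design cannot support.

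The factual part of this stands. The vaccine comparisons measure spillover, the composites contain the directly incentivised outcome, and the wording in sections 1 and 6 is loose. The inference to a needed change does not stand. The SAP calls its secondary analyses differences between groups, which is what they are, and it plans no claim about vaccine incentives. Spillover and total service uptake are reasonable secondary questions. Flu, COVID-19 and screening are each tested separately, so a composite driven by screening can be recognised from the planned output. The misreporting depends on an author overlooking the trial's own arm definitions.

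**Conclusion.** No change is needed. The randomised contrast is the $50 screening offer alone, and sections 1, 3 and 6 agree on it. The primary comparison matches that contrast exactly, and the four secondary tests are valid randomised comparisons. Following the plan as written gives sound results.

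The 3.2 to 16.0 and 0.8 to 12.0 point shifts depend on the assumed 20-point effect, on the assumed vaccine uptake and overlap, and on screening being independent of vaccination. They show a general property of composites that contain the primary outcome. The conclusion does not rest on them.

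What is left is loose wording in the last sentence of section 6 and the opening of the design paragraph in section 1. If the documents were reopened for another reason, the sponsor could say there that the screening card is what is tested and that the vaccine cards go to both arms, and could label the vaccine comparisons in the SAP as spillover. That would be a courtesy to readers; the design, the analysis and the results would be the same.
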